##### **7.2.4.3 Change from baseline in diffusion capacity of the lung for carbon monoxide (DLCO), corrected for HB, at 52 weeks**

Data from an external vendor with the DLCO result (mmol/min/kPa) will be used. The same analyses (ANCOVA) as detailed in Section 7.2.4.2 will be used but using the baseline DLCO rather than baseline 6MWT in the ANCOVA model.

Data collected at early withdrawal visit will be summarized descriptively only.

	Plus-Project Statistical Analysis Plan	
	Protocol Number: GALACTIC-1	Version: 1

7.2.4.4 Change from baseline at week 52 in dyspnea assessment by University of California San Diego - Shortness of Breath Questionnaire (UCSD - SOBQ)

Data from an external vendor with the UCSD – SOBQ scores will be used. The UCSD – SOBQ comprises of 24 items scored 0-5 where (0 = "not at all" to 5 = "maximal or unable to do because of breathlessness"). The item scores will be summed (treating any missing as 5) to derive a total score between 0 and 120. The UCSD – SOBQ items are provided in Section 11.7. The same MMRM analysis as detailed in Section 7.2.3.2 will be used for the change from baseline at week 52 in UCSD – SOBQ Total Score, using the baseline UCSD – SOBQ Total Score rather than the baseline SGRQ Total Score.

7.2.4.5 Change from baseline at Week 52 for HRQoL as assessed by Short Form Survey (SF-36)

Data from an external vendor with the SF-36 scores will be used. The change from baseline in SF-36 total score will be analyzed using an MMRM the same as detailed in Section 7.2.3.2 using the corresponding baseline SF-36 total score rather than the baseline SGRQ total score.

In addition, the actual and change from baseline in individual component scores as follows will be summarized by treatment group and visit:

- Physical component scale (PCS) and mental component scale (MCS).
- Physical functioning (PF), role physical (RF), bodily pain (BP), general health (GH), vitality (VT), social functioning (SF), role emotional (RE) and mental health (MH).

The details of scoring are provided in Section 11.8.

7.2.4.6 Percentage of subjects with Adverse Events (AE) or Serious Adverse Events (SAE) over 52 weeks

Only TEAEs with a start date prior to Day 379 will be considered for inclusion in the analysis. Summaries of the percentage of subjects with AE or SAEs will be presented for each population by SOC and PT. No formal analyses will be performed.

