### 11.8 SF-36 Scoring

The SF-36 (version 2) consists of 36 items. The 36 questions are:

1: In general, would you say your health is

2: Compared to one year ago, how would you rate your health in general now

3A: Vigorous activities, such as running, lifting heavy objects, participating in strenuous sports

3B: Moderate activities, such as moving a table, pushing a vacuum cleaner, bowling, or playing golf

3C: Lifting or carrying groceries

3D: Climbing several flights of stairs

3E: Climbing one flight of stairs

3F: Bending, kneeling, or stooping

3G: Walking more than a mile

3H: Walking several hundred yards

3I: Walking one hundred yards

3J: Bathing or dressing yourself

4A: As a result of your physical health, cut down on the amount of time you spent on work or other activities

4B: As a result of your physical health, accomplished less than you would like

4C: As a result of your physical health, were limited in the kind of work or other activities

4D: As a result of your physical health, had difficulty performing the work or other activities (for example, it took extra effort)

5A: As a result of any emotional problems, cut down the amount of time you spent on work or other activities

5B: As a result of any emotional problems, accomplished less than you would like

5C: As a result of any emotional problems, did work or other activities less carefully than usual

6: During the past 4 weeks, to what extent has your physical health or emotional problems interfered with your normal social activities with family, friends, neighbors, or groups

7: How much bodily pain have you had during the past 4 weeks

8: During the past 4 weeks how much did pain interfere with your normal work (including both work outside the home and housework)

9A: How much of the time during the past 4 weeks: did you feel full of life

9B: How much of the time during the past 4 weeks: have you been very nervous

	Plus-Project Statistical Analysis Plan		
	Protocol Number: GALACTIC-1	Version: 1	

9C: How much of the time during the past 4 weeks: have you felt so down in the dumps that nothing could cheer you up

9D: How much of the time during the past 4 weeks: have you felt calm and peaceful

9E: How much of the time during the past 4 weeks: did you have a lot of energy

9F: How much of the time during the past 4 weeks: have you felt downhearted and depressed

9G: How much of the time during the past 4 weeks: did you feel worn out

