9H: How much of the time during the past 4 weeks: have you been happy

9I: How much of the time during the past 4 weeks: did you feel tired

10: During the past 4 weeks, how much of the time has your physical health or emotional problems interfered with your social activities (like visiting your friends, relatives, etc.)

11A: I seem to get sick a little easier than other people

11B: I am as healthy as anybody I know

11C: I expect my health to get worse

11D: My health is excellent

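### The only SF-36 model in the SAP is fitted to a total score that is never defined, while the named physical and mental component scores get no treatment estimate

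*SAP*

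**What the plan says.** Protocol 9.3 lists change from baseline at week 52 in quality of life by SF-36 among the other secondary endpoints. It names the instrument but no score. Protocol 14.1 leaves the definition of analysis variables to the SAP.

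SAP 7.2.4.5 takes the scores from an external vendor and names one modelled variable: "The change from baseline in SF-36 total score will be analyzed using an MMRM the same as detailed in Section 7.2.3.2". The covariate is the baseline total. The remaining scores are handled descriptively: "In addition, the actual and change from baseline in individual component scores as follows will be summarized by treatment group and visit". The list that follows contains PCS, MCS and eight domain scores. The section closes with a pointer: "The details of scoring are provided in Section 11.8".

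Section 11.8 opens with "The SF-36 (version 2) consists of 36 items. The 36 questions are" and ends at "11D: My health is excellent". Everything between is item wording.

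An SF-36 total also appears among the baseline characteristics in SAP 6.2, again undefined. SAP Section 9, which records departures from the protocol, does not mention the SF-36.

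**The concern.** A modelled endpoint needs a stated derivation, a range and a direction, so that the sign and size of the treatment difference can be read from the plan. The SF-36 total has none of these.

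The items show why this matters. "9A: How much of the time during the past 4 weeks: did you feel full of life" and "9B: How much of the time during the past 4 weeks: have you been very nervous" run in opposite directions, as do 11A (getting sick more easily than others) and 11B (being as healthy as anyone known). Item 2 asks for a comparison with a year ago, so whether it belongs in a total at all needs a rule.

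SAP Section 5 says p-values will be produced for all efficacy comparisons. The report would therefore carry an SF-36 estimate and p-value on a scale that the plan does not describe. The two component scores that the SAP does name would have no between-group estimate. If the definition is left to the vendor or the programmer, it may also be settled after unblinding.

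**Working it through.** The plan states no figure on this point, so the check is a comparison of texts with some simple counting.

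**Step 1. Is Section 11.8 complete?** The items, by question number from 1 to 11, are 1 + 1 + 10 + 4 + 3 + 1 + 1 + 1 + 9 + 1 + 4 = 36. This matches the stated 36. The list is whole, and no missing-figure marker stands in that section, so nothing suggests that scoring text was lost.

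**Step 2. Can each questionnaire total be rebuilt from the SAP?**

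| Instrument | Scoring in the SAP | Rebuilt? |
|---|---|---|
| SGRQ (11.6) | Item weights, component maxima, missing-item rule | Yes |
| UCSD-SOBQ (7.2.4.4, 11.7) | Sum of 24 items scored 0 to 5, missing scored 5 | Yes |
| SF-36 (7.2.4.5, 11.8) | Item wording only | No |

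- SGRQ symptoms, using the largest weight for each of questions 1 to 8: 80.6 + 76.8 + 87.2 + 86.2 + 86.7 + 89.7 + 93.3 + 62.0 = 662.5, as stated.
- SGRQ activity, questions 11 and 15: 558.3 + 650.8 = 1209.1, as stated.
- SGRQ impacts, questions 9, 10, 12, 13, 14, 16 and 17: 83.2 + 88.9 + 493.4 + 663.4 + 293.5 + 398.7 + 96.7 = 2117.8, as stated.
- SGRQ total: 662.5 + 1209.1 + 2117.8 = 3989.4, as stated.
- UCSD-SOBQ maximum: 24 × 5 = 120, as stated.
- SF-36: with no response codes or aggregation rule, neither a maximum nor a direction can be computed for the total. The same is true of PCS, MCS and the domains.

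**Step 3. What does the choice of a total do?** Suppose, as an assumption, that the total is a weighted sum T = w₁·P + w₂·M of a physical part P and a mental part M. The treatment difference on T is then w₁·d₁ + w₂·d₂, where d₁ and d₂ are the differences on the two parts. A difference on one part is diluted when the other is zero and offset when the other has the opposite sign. The SAP gives neither the weights nor the form of the sum, so no size can be attached.

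**Step 4. Can the existing model be applied to PCS and MCS?** The mixed model for repeated measures (MMRM) in SAP 7.2.3.2 uses weeks 12, 26 and 52. It has treatment, visit, baseline score and treatment-by-visit as fixed effects. The schedule in SAP 11.2 collects SGRQ and SF-36 together, at baseline and those three visits. PCS and MCS are already to be summarised by visit. The model therefore carries over without new data.

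**The case against.** Several objections carry weight.

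- **PCS and MCS are no better defined than the total.** This is right. Section 11.8 scores none of them. A reader might infer that the SAP's own scoring yields interpretable component scores and an uninterpretable total, but the text does not support that ranking. Swapping the score without completing 11.8 would leave the gap open.
- **The vendor supplies scores, not raw items.** Also right. For UCSD-SOBQ the SAP says that it will sum the items, and it says nothing similar for SF-36. It is tempting to conclude that oppositely worded items will cancel. The documents do not show an unrecoded sum, so this remains a risk.
- **A total would not appear in a list of component scores, and the term is used consistently in 6.2 and 7.2.4.5.** Accepted. Its absence from that list proves nothing. The problem is that no section defines it.
- **The protocol names no score, so a total contradicts nothing.** True. The choice belongs to the sponsor, but it still has to be specified.
- **Diverging physical and mental results would show in the summaries.** Partly. The summaries would show group means and changes by visit, but give no modelled difference or interval.
- **The endpoint is minor.** True. It is one of eleven other secondary endpoints in protocol 9.3. The key secondary quality-of-life endpoint is the SGRQ total, which is fully defined.

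The undefined test variable and the absence of any estimate for the two named components survive these objections.

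**Conclusion.** The point holds in a limited form. The only SF-36 quantity that is modelled has no stated derivation, range or direction, and the section cited for its scoring contains none for any SF-36 score. PCS and MCS get no treatment difference or confidence interval.

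A reader might go further and say that the endpoint has no interpretable test at all. The documents do not establish that. A model and p-value will be produced, and a vendor score with a sound definition may exist outside the SAP. What can be said is that the result could not be interpreted from the plan as written. A single total would also pool the components that the SAP itself separates, however well it is recoded.

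The size cannot be quantified from the documents. The reach is one endpoint that protocol 14.4.2.2 treats as exploratory, with nominal p-values and no multiplicity adjustment. The primary and key secondary conclusions do not depend on it.

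The conclusion assumes that 11.8 is complete as published, which the item count supports. Whether an SF-36 total is recognised by the instrument's developers lies outside the documents and plays no part here.

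**What to change.** Before database lock and while still blinded:

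1. In SAP 7.2.4.5 and in the baseline list of 6.2, replace the SF-36 total with PCS and MCS.
2. Fit the 7.2.3.2 MMRM to each, with that score's own baseline as covariate. Report the week 52 treatment difference with its confidence interval, at the 90% and 95% levels that the SAP uses in 7.2.4.2.
3. Keep the eight domains descriptive.
4. In 11.8, state the vendor's scoring algorithm or version, the direction of each score and the missing-item rule.

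If the sponsor does want a total, the minimum is to define it in 11.8 to the same standard as the SGRQ total and give the reason for pooling.

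The cost is SAP wording, a request to the vendor for its scoring specification and one extra model in the Primary Population. A further run is needed if the per-protocol repeat in SAP Section 5 is taken to cover this endpoint. There would be two nominal p-values instead of one, with no multiplicity adjustment. No new data collection is needed.

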7.2.4.7 Time to first hospitalization (IPF related, including acute exacerbation of IPF)

The time to first hospitalization (IPF related, including acute exacerbation of IPF) will be derived from the ‘Exacerbation’ and ‘Adverse Events’ eCRF.

	Plus-Project Statistical Analysis Plan	
	Protocol Number: GALACTIC-1	Version: 1

If the subject was hospitalized and the AE linking to the hospitalization indicates that the PI/treating physician classed the AE as the result of an exacerbation of IPF then the hospitalization will be defined as being IPF related, including acute exacerbation of IPF.

The time to first hospitalization (IPF related, including acute exacerbation of IPF) in weeks will be derived as (date of first such hospitalization – date of randomization +1)/7.

If a patient does not require hospitalization (IPF related, including acute exacerbation of IPF) on or prior to Day 379, the same censoring rules will apply as in Section 7.2.3.3.

If there are fewer than 15 hospitalizations (IPF related, including acute exacerbation of IPF) then statistical analysis will not be performed, and only frequencies of hospitalizations by treatment group will be provided. Otherwise, the same analysis (Cox proportional hazards modelling) as detailed in Section 7.2.3.3 will be performed.

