6.2 Number of Participants

Approximately 141 participants in total will be randomized in GALACTIC-1.

Participants are considered evaluable if they have taken at least one dose of the double-blind treatment.

Participants who prematurely discontinue double-blind study treatment after randomization can remain in the study and complete the remaining scheduled visits, if possible.

Any participants who withdrawn from the study after randomization cannot be replaced and re-screened.

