9.3 Secondary endpoints

- Proportion of subjects with an absolute decline from baseline in FVC % pred of $\leq 5\%$ at w52.
- Change from baseline in 6-minute walk test (6MWT) distance over 52 weeks.
- Change from baseline in diffusion capacity of the lung for carbon monoxide (DLCO), corrected for HB, over 52 weeks.
- Change from baseline at week 52 for dyspnoea assessment by University of California San Diego - Shortness of Breath Questionnaire (UCSD - SOBQ).
- Change from baseline at week 52 for HRQoL as assessed by Short Form Survey (SF-36).
- Percentage of subjects with Adverse Events (AE) or Serious Adverse Events (SAE).
- Time to first hospitalization (IPF related, including acute exacerbation of IPF).
- Time to first hospitalization (all cause).
- Time to respiratory-related death.
- Time to initiation of nintedanib or pirfenidone.
- Change in FVC expressed in mL over 52 weeks for subjects who have never been treated with pirfenidone or nintedanib.

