18.3 Appendix 3. Definition of Acute Exacerbations in IPF

Acute respiratory worsening occurs in a small minority of patients with IPF annually (approximately 5–10%) [1-3]. These episodes may occur secondary to common conditions such as pneumonia, pulmonary embolism, pneumothorax, or cardiac failure [4]. When a cause cannot be identified for the acute respiratory decline, the term acute exacerbation of IPF has been used [3, 5-15]. It is presently unclear if acute exacerbation of IPF is simply a manifestation of an unidentified respiratory complication (such as pulmonary emboli, infection) contributing to an acute worsening in a patient with IPF or represents an inherent acceleration in the pathobiological processes involved in IPF.

Regarding the definition of AE in IPF, a revised "conceptual framework" was proposed by an international working group in 2016 [16].

The 2007 proposed definition of an "acute exacerbation" (AE) of IPF included all of the following:

- A previous or concurrent diagnosis of IPF
- Deterioration within 30 days
- New bilateral ground glass opacities and/or consolidation on a background of reticular or honeycomb pattern consistent with usual interstitial pneumonia (UIP)
- No evidence of pulmonary infection by endotracheal aspiration or bronchoalveolar lavage
- Exclusion of alternative causes including left heart failure, pulmonary embolism, or an identifiable cause of acute lung injury

The 2016 revised criteria more accurately reflect today's knowledge of AE-IPF and should allow for better insights into the etiology, treatment, and outcomes of this process [17]. Similar to the definition in 2007, this newly proposed framework defines an AE as "*an acute, clinically significant respiratory deterioration characterized by evidence of new widespread alveolar*

abnormality," but does not set an exact 30 day limit for symptom onset and does not require exclusion of infection. The following diagnostic criteria are proposed:

- A known diagnosis of IPF (diagnosis may be made at the time of acute respiratory deterioration)
- Acute worsening, "typically less than one month's duration"
- Computed tomography of the chest with new bilateral ground glass opacification and/or consolidation superimposed on a background of findings consistent with usual interstitial pneumonia (bibasilar reticular opacities associated with honeycomb changes and traction bronchiectasis)
- Heart failure or fluid overload does not fully explain the worsening.

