### 7.2.3.3 Time to first hospitalization (respiratory related, including acute exacerbation of IPF)

The time to first hospitalization (respiratory related, including acute exacerbation of IPF) will be derived from the 'Exacerbation' and 'Adverse Events' eCRF.

If the subject was hospitalized and the AE linking to the hospitalization indicates that the PI/treating physician classed the AE as the result of an exacerbation of IPF then the hospitalization will be defined as being respiratory related, including acute exacerbation of IPF.

Other respiratory related causes will be defined as all AEs in the 'Respiratory, Thoracic and Mediastinal Disorders' System Organ Class (SOC), plus those AEs in the 'Infections and Infestations' SOC with preferred terms containing the character strings 'resp', 'bronch', 'covid-19' or 'pneumo', or the specific PTs as follows:

- Influenza
- Legionella infection
- Viral infection

If a subject was hospitalized (respiratory related, including acute exacerbation of IPF) prior to or on Day 379 (Week 52 plus 2 weeks) then the  $(\text{date of first such hospitalization} - \text{date of randomization} + 1) / 7$  will be derived as the time to first hospitalization (respiratory related, including acute exacerbation of IPF) in weeks.

If a subject does not require hospitalization (respiratory related, including acute exacerbation of IPF) prior to or on Day 379, they will be censored in the analysis. The following censoring rules will be applied:-

- If lost to follow-up (LTFU), a subject will be censored at the earliest of date of last contact and Day 379
- If a subject discontinued (and not lost to follow-up), they will be censored at the earlier of the date of study discontinuation and Day 379.
- Otherwise, censor at the earliest of last contact date or Day 379.

	Plus-Project Statistical Analysis Plan	
	Protocol Number: GALACTIC-1	Version: 1

The superiority of GB0139 3mg compared to Placebo will be tested for the time to first hospitalization (respiratory related, including acute exacerbation of IPF).

The null hypothesis is:

$H_0$  : There is no difference in the time to first hospitalization between GB0139 3mg and Plc

The alternative hypothesis is:

$H_a$ : There is a difference in the time to first hospitalization between GB0139 3mg and Plc

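### SAP 7.2.4.7 counts an admission as IPF related only through the physician's exacerbation classification, so the derived endpoint is narrower than its name and the change is undeclared

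*SAP*

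**What the plan says.** Protocol 9.3 lists the endpoint as "Time to first hospitalization (IPF related, including acute exacerbation of IPF"), and SAP 2.2 repeats the name. The protocol leaves further detail on other secondary endpoints to the SAP (14.4.2.2).

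SAP 7.2.4.7 supplies the derivation. If a subject was hospitalised and the investigator or treating physician "classed the AE as the result of an exacerbation of IPF then the hospitalization will be defined as being IPF related", the admission is an event. No other qualifying route follows. The section then sets a floor: "If there are fewer than 15 hospitalizations (IPF related, including acute exacerbation of IPF) then statistical analysis will not be performed". Below it, only frequencies by treatment group are reported.

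SAP 7.2.3.3, for the key secondary respiratory-related endpoint, opens with the same exacerbation rule and then continues: "Other respiratory related causes will be defined as all AEs in the" respiratory system organ class, plus selected infection terms.

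SAP section 9 lists the departures from the protocol's analysis. The derivation of IPF-related hospitalisation is not among them.

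**The concern.** In the endpoint's name, exacerbation is a component of a wider class. In the derivation it is the whole class. An admission for worsening or progressive IPF that the physician does not class as an exacerbation leaves the subject event-free for this endpoint. If an exacerbation admission follows later, the event is dated to that later admission.

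The study report would then carry a result labelled IPF-related hospitalisation that measures only physician-classified exacerbation admissions. Admissions for progression, which a treatment aimed at slowing FVC decline might be expected to affect, would not contribute. A reader of the report would have no statement in section 9 to warn of this.

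**Working it through.** **1. The definitions side by side**

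| Endpoint | Route 1 | Route 2 |
|---|---|---|
| Respiratory related (SAP 7.2.3.3) | linked AE classed as result of an IPF exacerbation | coded to the respiratory class or a listed infection term |
| IPF related (SAP 7.2.4.7) | linked AE classed as result of an IPF exacerbation | none |
| All cause (SAP 7.2.4.8) | any hospitalisation | not needed |

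Take an admission whose AE reports worsening pulmonary fibrosis and is not classed as an exacerbation. All cause: event. Respiratory related: event if the AE is coded to the listed class or terms. IPF related: not an event. The SAP says *if* rather than *only if*, but a programmer has nothing else to implement.

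The size of this loss cannot be computed, because the documents give no rate of admission for IPF progression.

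**2. Side note: the 15-event floor**

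The documents state no expected number of IPF-related admissions. The inputs are:
- N = 141 (Protocol 6.2: "Approximately 141 participants in total will be randomized in GALACTIC-1").
- Follow-up to Day 379 (SAP 5.2).
- Annual risk of 5–10%, from Protocol Appendix 3: "Acute respiratory worsening occurs in a small minority of patients with IPF annually", with that range given in brackets.

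The source of N reproduces. With 47 and 94 subjects, a 100 mL difference, SD 240 mL and two-sided 10%, SE = 240 × √(1/47 + 1/94) = 42.9 mL. Then 100/42.9 − 1.645 = 0.69, which gives 75.4% power against the stated 75%.

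Risk to Day 379 = 1 − (1 − p)^(379/365.25). Expected subjects with an event = N × risk. The chance of missing the floor is the binomial P(X ≤ 14).

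| Annual p | Risk to Day 379 | Expected, N = 141 | P(fewer than 15) |
|---|---|---|---|
| 5% | 5.18% | 7.3 | 99% |
| 7.5% | 7.77% | 11.0 | 87% |
| 10% | 10.36% | 14.6 | 50% |

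**3. Sensitivity of the side note**

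- *Share admitted and classed as exacerbation.* The 5–10% covers acute worsening with or without admission, before dropout. If 80% led to a qualifying admission (an assumption), the chance of a miss is 97% at 7.5% and 81% at 10%.
- *N.* SAP 1.1 says about 141 are enrolled into the modified design, and SAP 1.3 adds original-design SoC2 subjects on placebo or 3 mg. If the 141 are all new and join about 320 − 200 = 120 continuing subjects, N is about 261 (an assumption). Expected subjects with events are then 13.5, 20.3 and 27.0, and the chance of a miss is 62%, 9% and 0.3%.

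**The case against.** **The consequence is limited.** This is an other secondary endpoint, exploratory and with nominal p-values (Protocol 14.4.2.2). The admissions in question are not lost to the trial: they count as all cause and, where suitably coded, as respiratory related. SAP 7.3.2 also tabulates serious events by class and term. Below the floor, frequencies are still shown. All of this stands. It limits the importance of the point but does not align the derivation with the name.

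**A reader might infer that the narrow rule is what pushes the count below 15.** The documents do not support that. It would need a count under the wider definition, and there is none; the wider definition might also fall short. The projection shows only that events may be few. It is close to an even chance at 10%, and it reverses for most of the range if N is about 261. The 5–10% is a general IPF figure, and the rate in a population not on antifibrotics at entry could differ. The floor is also worded in hospitalisations, whereas the projection counts subjects, so repeat admissions, if counted, would make it slightly easier to reach.

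**A reader might also infer that an admission without new CT opacities is excluded by rule.** It is not. SAP 7.2.4.7 relies on the physician's classification and does not invoke the Appendix 3 criteria. Protocol 12.2 refers to that appendix for adjudication that is optional and follows read-out. The CRF wording is not available, so how physicians will class progression admissions is unknown.

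**Nor should exacerbations be taken as only a small part of the 5–10%.** Appendix 3 reports one usage confined to unexplained events ("When a cause cannot be identified for the acute respiratory decline, the term acute exacerbation of IPF has been used"), but the 2016 criteria it also describes admit triggers such as infection, which narrows the gap.

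**Conclusion.** The point holds on the text alone, without any assumption about rates. The derivation in SAP 7.2.4.7 is narrower than the endpoint named in Protocol 9.3 and SAP 2.2, it lacks the second limb that 7.2.3.3 has, and the narrowing is not declared in section 9. Its size in events is unknown, and its reach is one exploratory endpoint.

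The floor is a secondary observation. At N = 141 and 5–10% a year, about 7 to 15 subjects with events are expected by Day 379, so the Cox analysis may well not be run. That rests on the reading of N and on a borrowed rate, and it is not evidence that the definition causes the shortfall.

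**What to change.** In SAP 7.2.4.7, count a hospitalisation as IPF related if its linked AE is either:

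- (a) classed by the physician as the result of an IPF exacerbation; or
- (b) coded to a preferred term denoting the disease itself, for example idiopathic pulmonary fibrosis, pulmonary fibrosis or its progression.

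Fix the term list blinded at the data review meeting. Admit non-specific terms such as respiratory failure or hypoxia only where blinded case review can attribute them to IPF. The attributions the documents show are relationship to study drug, the IPF-exacerbation classification and a COVID flag, so coded terms alone cannot do this. Report the exacerbation-only version as a component.

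If the sponsor prefers to keep the present rule, rename the endpoint *hospitalisation for physician-classified exacerbation of IPF* and record the change in SAP section 9.

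The cost is a few lines of SAP text and one term list at a meeting already planned before database lock (SAP 1.2 and 4.6), using AEs that will be MedDRA-coded anyway. Blinded case review is extra work, needed only if non-specific terms are included. No new data collection is needed, and the primary analysis is unchanged.
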